## SYNOPSIS

Title	Efficacy of Nitric Oxide in Stroke-2 (ENOS-2)
Acronym	ENOS-2
Short title	Efficacy of Nitric Oxide in Stroke-2 (ENOS-2)
Chief Investigator	[name] Deputy Chief Investigator: [name]
Objectives	To assess the feasibility of recruitment and safety of transdermal glyceryl trinitrate (GTN) versus sham applied between 3 and 5 hours of stroke to inform a definitive trial.
Trial Configuration	Prospective randomised single-blinded masked-endpoint phase IIb trial.
Setting	Adults with hyperacute stroke presenting at emergency departments and hyperacute stroke units in England.
Sample size estimate	This is a feasibility study so there is no formal sample size calculation. (But recruitment of 100 participants would allow an adjusted common odds ratio, acOR 0.51 to be detected, assuming mRS distribution as in  ; alpha 0.05, power 0.80.)  It is likely that a large definitive trial would be feasible if at least 70 participants were recruited into this study. Lower recruitment would not preclude progression if there was some evidence that the barriers to recruitment identified could be overcome.
Number of participants	
 
• 100 with ischaemic stroke (50 randomised to GTN, 50 randomised to sham)
 
• 20 with intracerebral haemorrhage (for safety) (10 randomised to GTN, 10 randomised to sham)
 

Eligibility criteria	
Inclusion:  120 adults (≥18 years) with presentation compatible with stroke  Treatment 3-5 hours post ictus (for patients with wake-up stroke, treatment no more than 5 hours after patient awakens)  One or more of the following symptoms present at time of enrolment:  Dysphasia, neglect (NIHSS 1-2), hemianopia (NIHSS 1-3), or limb weakness (NIHSS on affected arm and/or leg 1-4)  Systolic BP (≥120 mmHg)  If a CT/MR scan has already been performed, then it shows acute intracerebral haemorrhage or ischaemic stroke, or is normal.  Waiver of consent for treatment to ensure GTN given in 3-5-hour time-window (and thrombolysis not delayed if ischaemic stroke).
 
Exclusion:  mRS ≥4  Glucose (BM stix or equivalent) <3 mmol/l  Glasgow coma scale ≤8  Witnessed seizure at presentation  Known life expectancy <6 months.  Patient presenting with sensory symptoms only  Known stroke mimic, aneurysmal subarachnoid haemorrhage, or haemorrhage due to venous thrombosis  Systolic blood pressure <120 mmHg  Known allergy to glyceryl trinitrate (Transiderm-Nitro) patch  Known sensitivity to Duoderm hydrocolloid dressing  Planned for palliative care only  Recent use of phosphodiesterase type 5 (PDE5) inhibitors, e.g., sildenafil (Viagra®)  If a CT/MR scan has already been performed, then it shows a non-stroke lesion that explains the acute presentation  Known previous enrolment in ENOS-2

Description of interventions	
Active: Transdermal glyceryl trinitrate (GTN) 5 mg placed on back or shoulders and applied for 2 days  Comparator: Transdermal Duoderm hydrocolloid dressing placed on back or shoulders and applied for 2 days.

Duration of study	
The trial will last 36 months (until May 2024), with recruitment occurring over 31 months (until February 2024). Once enrolled, participants will be treated for 2 days, and followed-up at 90 (primary outcome).

Randomisation and blinding	
Patients will be randomised (1:1) to receive either glyceryl trinitrate patches or sham patches. Randomisation will be performed by the Nottingham Stroke Trials Unit (STU) and involve computerised stratification by stroke type (IS or not known; ICH) and minimisation on age, severity, time, systolic blood pressure and candidate for or received reperfusion therapy. Patients, relatives, researchers and outcome assessors will be masked to treatment allocation.

Outcome measures	
Feasibility outcome
 
 
Recruitment of 100 IS patients, 20 ICH patients
 
 
Mechanistic outcomes
 
 
Blood pressure (BP) and heart rate (HR) over first 2 days
 
Bloods
 
 
Clinical outcomes
 
Day 2
 
 
Impairment
 
 
Discharge or death
 
 
Discharge destination
 
 
Day 90
 
 
Functional outcome: modified Rankin Scale (mRS = primary clinical outcome)
 
Disability (Barthel index, BI), cognition (telephone TICS, MMSE), mood (Zung depression scale, ZDS), quality of life (Euro-QoL EQ-5D and EQ-VAS).
 
 
Safety outcomes
 
 
Serious adverse events (SAEs) up to day 2 (i.e., 48 hours after 1st patch applied; fatal SAEs to day 90.
 
Death
 

Statistical methods	
This is a feasibility trial, and the main analysis will be with descriptive statistics only. Counts will be summarised using N and %, and continuous variables will be summarised using means (standard deviation) or median [interquartile range] depending on their distribution. Mechanistic, clinical and safety outcomes will be compared between the treatment groups using binary logistic regression, Cox proportional hazards regression (death), ordinal logistic regression (mRS) or multiple linear regression (BI, TICS, t-MMSE, ZDS, EQ-5D, EQ-VAS, as appropriate, in exploratory analyses.

## ABBREVIATIONS

ADR	Adverse Drug Reaction
AE	Adverse Event
A&E	Accident & Emergency
AI	Augmentation Index
ASPECTS	Alberta Stroke Program Early CT score
BI	Barthel Index
BP	Blood pressure
CE	Cardio-embolic
CF	Informed Consent Form
CI	Chief Investigator
CRF	Case Report Form
CT	Computerised Tomography
CTA	CT angiography
CTP	CT perfusion
DBP	Diastolic Blood Pressure
DMC	Data Monitoring Committee
eCRF	Electronic CRF
ED	Emergency Department
EMAS	East Midlands Ambulance Service
EQ-5D	Euro Quality of Life-5 Dimensions
EQ-VAS	Euro Quality of Life-Visual Analogue Scale
EOT	End of Trial
FAST	Face, Arm, Speech, Time test
GCP	Good Clinical Practice
GTN	Glyceryl Trinitrate
HR	Heart Rate
HUS	Health Utility Status
ICH	Intracerebral Haemorrhage
IMP	Investigational Medicinal Product
IMPD	Investigational Medicinal Product Dossier
IS	Ischaemic Stroke
ITT	Intention to treat
LACS	Lacunar syndrome
LAD	Large artery disease
MHRA	Medicines and Healthcare products Regulatory Agency
MMSE	Mini-Mental State Examination
MRI	Magnetic Resonance imaging
MRA	MR angiography
mRS	Modified Rankin Scale
NHS	National Health Service
NIHSS	National Institutes of Health Stroke Scale
NK	Not Known
NO	Nitric oxide
NTG	Nitroglycerin
NUH	Nottingham University Hospitals NHS Trust
PACS	Partial anterior circulation syndrome

PI	Principal Investigator (at a local centre)
PIS	Participant Information Sheet
POCS	Posterior circulation syndrome
PP	Per protocol
QP	Qualified Person
REC	Research Ethics Committee
R&D	Research and Development department
SAE	Serious Adverse Event
SAP	Statistical Analysis Plan
SAR	Serious Adverse Reaction
SBP	Systolic Blood Pressure
SPC	Summary of Product Characteristics
SUSAR	Suspected Unexpected Serious Adverse Reaction
SVD	Small vessel disease
TACS	Total anterior circulation syndrome
TCD	Transcranial Doppler
TIA	Transient Ischaemic Attack
TICS	Telephone Interview Cognition Scale
TMC	Trial Management Committee
TSC	Trial Steering Committee
UoN	University of Nottingham
ZDS	Zung Depression Scale

## TRIAL / STUDY BACKGROUND INFORMATION AND RATIONALE

**Stroke:** Is common (life-time risk 1/5-6) and devastating (death 25%, dependency 40% at 1 year). Acute treatment is limited to alteplase, mechanical thrombectomy, aspirin, hemispherectomy and stroke unit care. Anticoagulation is ineffective, neuroprotection unproven, and there is no widely-agreed treatment for intracerebral haemorrhage (ICH) although lowering blood pressure (BP) may be beneficial. Developing new interventions in hospitals has failed, in part, due to delayed treatment beyond the 'golden' hour after stroke. The management of physiological disequilibrium - BP, oxygen, glucose, cerebral oedema - remains unclear, and it is reasonable to hypothesise that their treatment, if warranted, should start rapidly after stroke onset.

**High BP:** Is common (80%) in patients with acute IS and ICH, and is associated independently with increased early recurrence and late death or dependency. Whether lowering BP improves outcome through reducing expansion and recurrence, or worsens it through reducing cerebral blood flow (due to dysfunctional autoregulation) remains unclear, in part because most trials started treatment several hours after onset. When assessing functional outcome, trial results have varied from a strong positive trend (INTERACT-2: SBP 14 mmHg lower with intensive treatment in ICH) through neutral effect (IMAGES: BP 4/3 mmHg lower with intravenous magnesium in mixed IS/ICH; CATIS: systolic BP 9 mmHg lower with intensive treatment in IS; ENCHANTED-BP SBP 5.5 mmHg lower with intensive BP-lowering in IS) to strong negative trend (BEST: oral propranolol or atenolol in mixed IS/ICH; INWEST: intravenous nimodipine in IS; SCAST: BP 5/2 mmHg lower with oral candesartan in mixed IS/ICH). Meta-analysis, and meta-regression of trial outcomes versus BP change, have not identified benefit.

**Nitric oxide (NO) and donors such as glyceryl trinitrate (GTN):** Are candidate treatments for acute stroke and multiple mechanisms exist by which they might be effective; taken together, these actions may 'buy time' for the brain, protect it and prime patients for arterial reperfusion therapies:

- NO/GTN lowers BP in acute/subacute stroke and so may 'move' patients down the epidemiological curve relating high BP and poor outcome. This mechanism may be of particular relevance in ICH.
- NO dilates cerebral arteries (e.g. middle cerebral) so could increase 'front door' cerebral blood flow (CBF) and peri-lesional perfusion, as seen in the GTN-3 pilot trial.
- NO dilates pial arteries (shown experimentally) so might increase CBF via the 'back-door'.
- NO donors are neuroprotective in preclinical stroke, especially if given early.
- Endogenous NO levels are low in acute stroke; hence, administration will supplement low [NO].
- GTN may 'prime' patients for rt-PA by lowering their BP so that more can be treated, and more rapidly after hospital arrival. RIGHT showed non-significant trends for these.
- GTN, through cerebral vasodilation, may increase access of alteplase to obstructing clot and therefore increase the effectiveness of thrombolysis, i.e., GTN might be additive to rt-PA.

Several NO donors are licensed in the UK and are used widely in patients with ischaemic heart disease, heart failure and severe hypertension; these include intravenous sodium nitroprusside and transdermal glyceryl trinitrate. One uncontrolled pilot study found that sodium nitroprusside lowered BP without altering cerebral perfusion (assessed using CT SPECT), and attenuated platelet function, in patients with recent ischaemic stroke. Four

phase II and two phase III randomised controlled trials have assessed transdermal glyceryl trinitrate in patients with acute stroke (IS and ICH) (Table 1).

**Table 1. Characteristics of completed trials of transdermal glyceryl trinitrate.**

	GTN-1 30	GTN-2 31	GTN-3 24	RIGHT 28,32,33	ENOS 2,34-36	RIGHT-2 3,37-40
Setting	Hospital	Hospital	Hospital	Pre-hospital	Hospital	Pre-hospital
Time window (hr)	<120 hours	<72 hours	<120 hours	<4 hours	<48 hours	<4 hours
Stroke type	IS/ICH	IS/ICH	IS/ICH	IS/ICH	IS/ICH	IS/ICH
SBP range (mmHg)	No limits	100-230	140-220	>140	140-220	>120
Treatment blinding	Double-blind	Open-label	Single-blind	Single-blind	Single-blind	Single-blind
GTN dose (mg)	5	5/10	5	5	5	5
Thrombolysis given	N/A	N/A	N/A	After GTN	Before GTN	After GTN
Sample size						
Intended	38	90	18	80	>3500	850
Achieved	37	90	18	41	4011	1149

ICH: intracerebral haemorrhage; IS: ischaemic stroke; N/A: not applicable; SBP: systolic blood pressure

GTN lowered BP, increased heart rate, and did not alter cerebral blood flow (assessed using xenon CT) or platelet function. The safety and efficacy of GTN in patients with acute stroke (IS, ICH) has been assessed in two large phase III trials.

**International hospital-based MRC ENOS trial:** In comparison with no GTN, transdermal GTN was not associated with any difference in functional outcome (mRS), disability/Activities of Daily Living (BI), cognition (tMMSE, TICS, animal naming), mood (ZDS) or quality of life (EQ-5D/HUS, EQ-VAS) (Table 2). No safety issues were found with GTN.

In the subgroup of patients randomised within 6 hours of ictus (average time from event to randomisation 263 minutes) (identified here as 'ENOS-early'), treatment with GTN was associated with reduced death, and improved functional outcome (mRS, BI) and quality of life (Table 2).

**UK ambulance-based BHF RIGHT-2 trial:** The average time to treatment was 70 minutes. In comparison with sham, transdermal GTN was not associated with any differences in functional outcome (mRS), disability/Activities of Daily Living (BI), cognition (tMMSE, TICS, animal naming), mood (ZDS) or quality of life (EQ-5D/HUS, EQ-VAS).

**Table 2. Outcomes in patients treated with GTN versus no GTN/sham**

Data are number (%), median [interquartile range] or mean (standard deviation). Analysis with binary logistic regression (odds ratio), ordinal logistic regression (odds ratio) or multiple regression (mean difference).

Outcome measure	GTN	No GTN	OR/MD (95% CI)	p
ENOS (OTR 0-48 hours) 				
Modified Rankin Scale (/6)	3 [3]	3 [3]	1.01 (0.91, 1.13)	0.83
Barthel Index (/100)	66 (38)	63 (39)	2.18 (-0.23, 4.59)	0.11
EQ-VAS (/100)	57 (31)	56 (32)	0.8 (-1.3, 2.9)	0.70
Death (%)	233 (12)	263 (13)	0.89 (0.72, 1.10)	0.27
ENOS-early (OTR 0-6 hours) 				
Modified Rankin Scale (/6)	3 [3]	3 [3]	0.53 (0.34, 0.82)	<0.001
Barthel Index (/100)	74 (34)	60 (41)	14 (4.6, 22.5)	0.01
EQ-VAS (/100)	62 (29)	53 (35)	9.6 (1.8, 17.5)	0.03
Death (%)	11 (8)	26 (20)	0.35 (0.13, 0.96)	0.04
RIGHT-2 (OTR 0-4 hours) 				
Modified Rankin Scale (/6)	3 [3]	3 [3]	1.25 (0.97, 1.60)	0.083
Barthel Index (/100)	56 (45)	58 (44)	-3 (-8, 2)	0.29
EQ-VAS (/100)	45 (34)	47 (32)	-0.9 (-5.1, 3.2)	0.66
Death (%)	97 (23)	79 (19)	1.24 (0.91, 1.86)	0.17

CI: confidence intervals; EQ-VAS: EuroQoL-Visual Analogue Scale; ICH: intracerebral haemorrhage; IS: ischaemic stroke; MD: mean difference; N/A: not applicable; OR: odds ratio; SBP: systolic blood pressure.

The following summary observations can be made based on data from the four phase II and two phase III GTN trials:

[figure not shown]
- Transdermal administration is advantageous since oral treatment is confounded by dysphagia in 50% of patients with acute stroke, whilst intravenous therapy requires intensive monitoring. Additionally, treatment can be stopped and restarted according to need.
- Peak concentrations of GTN are achieved by 1-2 hours.
- Transdermal GTN lowers systolic BP significantly by 15, 60 and 120 minutes.
- Transdermal GTN lowers central and peripheral SBP, DBP and pulse pressure; peak systolic BP and augmentation index; and 24-hour BP in both dipping and non-dipping patients.
- Transdermal GTN is feasible to administer, well tolerated, and safe when given early after acute stroke.
- GTN does not alter platelet function; hence, it can be given in ICH as well as IS.
- GTN does not reduce cerebral blood flow.
- GTN is safe in patients with severe carotid stenosis.

Further, the effect of GTN on functional outcome appears to be time-dependent when administered after stroke:

[figure not shown]
- <2.0 hours: No effect; indeed, GTN may cause harm in ICH in this ultra-acute period (interpretation from RIGHT-2 )
- 2.5 to 5.5 hours: May improve functional outcome (interpretation from ENOS-early  and meta-analysis, Figures 1 , 2).
- >6 hours: No effect (interpretation from GTN 1/2/3 and ENOS and an individual patient data meta-analysis ).

(The positive effect of GTN on functional outcome in the phase II RIGHT trial is ignored here because it was small.)

**Figure 1. Meta-analysis of GTN versus no GTN on end of trial functional outcome in patients treated within 6 hours of stroke onset (from )**

**Figure 2. Meta-analysis of GTN versus no GTN on end of trial death in patients treated within 6 hours of stroke onset (from )**

In summary, GTN has been associated with beneficial effects on function and other clinical outcomes in hospitalised patients treated up to 6 hours after ictus. However, benefit was not seen in patients treated prior to hospital admission and there was weak evidence that ultra-acute treatment within 2 hours was associated with harm. As a result, ENOS-2 will assess, in a novel design, the feasibility of recruiting patients between 3 and 5 hours after ictus; if feasible, a larger safety and efficacy trial will be performed in this group of patients.

ENOS-2 will assess the feasibility, safety, and efficacy of hospital-delivered GTN when administered hyper-acutely after stroke. Five of the six GTN trials had a lower limit for systolic blood pressure of  $\geq 100$  mmHg,  $>120$  mmHg or  $\geq 140$  mmHg, the first study had no lower limit. Since several potential mechanisms by which GTN might work are BP-independent, ENOS-2 will follow the RIGHT-2 protocol and include patients with high-normal BP as well as high BP, with a lower limit set to  $\geq 120$  mmHg. This has the advantage that the results will apply to a wider population of stroke patients and include more patients with severe stroke (some of whom have SBP  $<140$  mmHg).

## DETAILS OF INVESTIGATIONAL MEDICINAL PRODUCT(S)

### Description

The investigational medicinal product (IMP) is transdermal glyceryl trinitrate patch (GTN, - Transiderm-Nitro '5' (Novartis). GTN is also known as nitroglycerin (NTG). One patch will be given on 2 consecutive days. Further chemical and pharmacological properties of the GTN patch - Transiderm-Nitro '5' are provided in a separate Summary of Product Characteristics document (SmPC).

The GTN patch will be placed on the shoulders or back and the position rotated daily. GTN patches will be covered with a gauze dressing to mask the patient to treatment.

### Manufacture

The GTN patch Marketing Authorisation Holder is Novartis Pharmaceuticals Ltd.  
[PL 00101/0464](#)

### Packaging and labelling

Active patches will not be removed from their primary packaging. For blinding purposes, active patches will be packed with a gauze dressing into a plain opaque pouch which will be heat sealed by Pharmacy Production, Nottingham University Hospitals NHS Trust MIA(IMP): 19162. The manufacture will be in accordance with cGMP. Groups of 2 pouches will be assigned a pack number and these pouches will be packed into a labelled carton with the same pack number. The outer pouches and carton will be labelled according to Annex 13 - the Rules Governing Medicinal Products in the European Union, Volume 4. Labels will state usage instructions and storage conditions for the IMP.

The final product will be QP released by the designated person to provide blinded trial treatment packs for use in the trial.

### Storage, dispensing and return

NUH Clinical Trial Pharmacy will act as the central distribution pharmacy and receive, and store blinded packs from Pharmacy Production. Pharmacy will send packs to the participating stroke units.

Each participating research coordinator will take and sign-out one numbered pack following consent and randomisation. When a pack is assigned to a participant, the coordinator will add the Participant's name and date dispensed to the label. If the pack has been assigned, the coordinator will complete the Use/Non-use Form. If the pack has been assigned but the IMP was not used (e.g., if the participant changed their mind after consenting but before application of the patch), the coordinator will explain on the Use/Non-use Form why treatment was not administered and return the pack to the Nottingham Pharmacy.

Trial treatment must not be used for any other purpose than the present study. Any part-used packs will be returned to NUH for disposal. Returned trial medication that has been assigned to a participant must not be re-dispensed to a different participant.

### Known Side Effects

**Table 3. Known side effects of the IMP**

Nervous System Disorders:	
Common:	Headache
Very rare:	Dizziness
Cardiac Disorders:	
Rare:	Tachycardia
Vascular Disorders:	
Rare:	Orthostatic hypotension, flushing
Gastrointestinal Disorders:	
Very Common:	Nausea, vomiting
Skin and subcutaneous tissue disorders:	
Uncommon:	Contact dermatitis
General disorders and administration site conditions:	
Uncommon:	Application site erythema, pruritus, burning, irritation.
Investigations:	
Rare:	Heart rate increase

NB. Very common ( $\geq 1/10$ ); common ( $\geq 1/100$ ,  $<1/10$ ); uncommon ( $\geq 1/1000$ ,  $<1/100$ ); rare ( $\geq 1/10,000$ ,  $<1/1000$ ); very rare ( $<1/10,000$ ), including isolated reports.

Contraindications to the IMP are as follows:

- Known hypersensitivity to glyceryl trinitrate/nitroglycerin, and related organic nitrates or any excipient.
- Acute circulatory failure associated with marked hypotension (shock).
- Conditions associated with elevated intracranial pressure.
- Myocardial insufficiency due to obstruction, as in aortic or mitral stenosis, or constrictive pericarditis.
- Concomitant use with a phosphodiesterase type 5 (PDE5) inhibitor such as sildenafil (Viagra®) because PDE5 inhibitors may amplify the vasodilatory effects of GTN resulting in severe hypotension.
- Severe hypotension (systolic blood pressure less than 90 mmHg).
- Severe hypovolaemia.

The following interactions are possible:

- Concomitant administration with other vasodilators e.g., PDE5 inhibitors such as sildenafil potentiate the blood pressure lowering effects of GTN.
- Concomitant treatment with calcium antagonists, ACE inhibitors, beta-blockers, diuretics, antihypertensives, tricyclic antidepressants and major tranquillisers may potentiate the blood pressure-lowering effect of GTN, as may alcohol.
- Concurrent administration with dihydroergotamine may increase the bioavailability of dihydroergotamine. This warrants special attention in patients with coronary artery disease, because dihydroergotamine antagonises the effect of GTN/nitroglycerin and may lead to coronary vasoconstriction.
- Non-steroidal anti-inflammatory drugs, except acetyl salicylic acid, may diminish the therapeutic response of Transiderm-Nitro.

- Concurrent administration with amifostine and acetyl salicylic acid may potentiate the blood pressure lowering effects of Transiderm-Nitro.

Reference source: SPC:

<http://www.medicines.org.uk/emc/medicine/1333/SPC/Transiderm-Nitro 5 and 10>

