## **RANDOMISATION AND BLINDING**

All participants eligible for inclusion will be randomised centrally using a secure internet site in real-time. Randomisation will be 1:1 GTN: sham and involve computerised stratification by stroke type (ischaemic stroke or not known vs ICH) and minimisation on age, severity, time, systolic blood pressure and candidate for or received reperfusion therapy (alteplase, and/or mechanical thrombectomy). This approach ensures concealment of allocation, minimises differences in key baseline prognostic variables, and slightly improves statistical power (16). Patients, relatives, researchers, and outcome assessors will be masked to treatment allocation.

In order to minimise selection bias, a participant must be enrolled in the study before they are randomised on the internet site. Randomisation will allocate a number corresponding to a treatment pack and the participant will receive treatment from the allocated numbered pack.

In the event of computer failure (for example: server failure), investigators will follow the working practice document for computer system disaster recovery, which will allow the participant to be randomised following standardised operating procedure.

Personnel applying the GTN/sham patches will not be blinded to the treatment allocation as the sachets around the patches are different and carry the manufacturers identifying information.

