### **Exclusion criteria**

- mRS  $\geq 4$
- Hypotension or shock (systolic  $< 120$  mmHg)
- BP Glucose (BM stix or equivalent)  $< 3$  mmol/l
- Glasgow coma scale  $\leq 8$
- Witnessed seizure at presentation
- Known life expectancy  $< 6$  months
- Patient presenting with sensory symptoms only
- Known stroke mimic, aneurysmal subarachnoid haemorrhage, or haemorrhage due to venous thrombosis
- Known allergy to glyceryl trinitrate (Transiderm-Nitro) patch
- Known sensitivity to Duoderm hydrocolloid dressing
- Planned for palliative care only
- Recent use of phosphodiesterase type 5 (PDE5) inhibitors, e.g., sildenafil (Viagra®)
- If a CT/MR scan has already been performed, then it shows a non-stroke lesion that explains the acute presentation
- Known previous enrolment in ENOS-2

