### Concomitant and Rescue Medications and Treatments

The intervention (GTN or sham) will be given in addition to routine care. There are no prohibited concomitant treatments.

No publications have been found that would suggest a contraindication as a result of the interaction between the IMP and the COVID-19 vaccine.

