### **Protocol Violation**

A protocol violation is a usually major deviation from the expected trial regimen such as where a participant is enrolled in spite of not fulfilling all the inclusion and exclusion criteria, or where deviations from the protocol could affect the trial delivery or interpretation significantly.

All protocol deviations and violations must be reported immediately to the Chief Investigator, via the online electronic case report form. The CI will notify the Sponsor if a deviation or violation has an impact on participant safety or integrity of the trial data. The Sponsor will advise on appropriate measures to address the occurrence, which may include reporting of a serious GCP breach, internal audit of the trial and seeking counsel of the trial committees.

Examples of protocol violations are given below but this list is not exhaustive:

- Day 2 follow-up performed >7 days past due date

- Death/discharge form entered >14 days after event
- Day 90 follow-up performed <80 days or >120 days past due date
- Participant enrolled in spite of not fulfilling all the inclusion and exclusion criteria
- Aneurysmal subarachnoid haemorrhage known at time of randomisation
- Non-stroke diagnosis, known at time of randomisation
- Failure to complete SAEs where appropriate
- Management of IMP – treatment pack lost

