**20b Exclusion**

1. mRS  $\geq 4$
2. Glucose (BM stix or equivalent)  $< 3$  mmol/l
3. Glasgow coma scale  $\leq 8$
4. Witnessed seizure at presentation.
5. Known life expectancy  $< 6$  months.
6. Patient presenting with sensory symptoms only.

7. Known stroke mimic, aneurysmal subarachnoid haemorrhage, or haemorrhage due to venous thrombosis.
8. Systolic blood pressure <120 mmHg
9. Known allergy to glyceryl trinitrate (Transiderm-Nitro) patch.
10. Known sensitivity to Duoderm hydrocolloid dressing.
11. Planned for palliative care only.
12. Recent use of phosphodiesterase type 5 (PDE5) inhibitors, e.g., sildenafil
13. If a CT/MR scan has already been performed, then it shows a non-stroke lesion that explains the acute presentation.
14. Known previous enrolment in ENOS-2

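### The protocol contraindicates the GTN patch in myocardial insufficiency due to obstruction, but no exclusion criterion covers it

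*Protocol*

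**What the plan says.** Under Known Side Effects, after Table 3, the Protocol lists seven contraindications to the study patch. One is "Myocardial insufficiency due to obstruction, as in aortic or mitral stenosis, or constrictive pericarditis". Another is "Concomitant use with a phosphodiesterase type 5 (PDE5) inhibitor such as sildenafil (Viagra".

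Eligibility is set out in three places: the Protocol Synopsis, the Protocol's Exclusion criteria section and SAP section 20b. Each gives the same 14 exclusions, with small differences of wording. Those that bear on the contraindications are a systolic pressure below 120 mmHg, "Known allergy to glyceryl trinitrate (Transiderm-Nitro) patch" and "Recent use of phosphodiesterase type 5 (PDE5) inhibitors, e.g., sildenafil". The remaining exclusions concern pre-stroke function, glucose, consciousness, seizure, prognosis, sensory-only presentation, mimics and other haemorrhage types, the sham dressing, palliative care, scan findings and previous enrolment.

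On treatment given alongside the patch, the Protocol says "There are no prohibited concomitant treatments".

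**The concern.** The eligibility list is what a site works from when it decides whether to enrol. Here the Protocol states that the product should not be used in a particular cardiac condition, and the list does not ask about it. Three other contraindications are screened for, so the gap looks like an omission; the documents give no reason for leaving this condition out.

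The stake is patient safety at entry. A site applying the criteria as written could put a GTN patch on a patient for whom the same Protocol says it is contraindicated. Hypotension needing intervention is a safety endpoint, and cardiovascular serious adverse events are tabulated in SAP Table 9, but both are recorded only after the patch has been applied. Enrolment must fit a two-hour window and may proceed without prior consent from a patient who lacks capacity and has no relative present, so an explicit prompt to check the known history is useful.

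**Working it through.** No formula applies. The check sets each contraindication against the eligibility criteria.

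| Contraindication (Protocol, Known Side Effects) | Matching criterion | Status |
|---|---|---|
| Hypersensitivity to GTN, related organic nitrates or excipients | Known allergy to the GTN patch | Partly covered: other organic nitrates not named |
| Shock with marked hypotension | Systolic pressure below 120 mmHg | Covered |
| Raised intracranial pressure | None | No match; ICH is enrolled by design |
| Myocardial insufficiency due to obstruction | None | Not covered |
| Concomitant PDE5 inhibitor | Recent PDE5 inhibitor use | Covered at entry |
| Systolic pressure below 90 mmHg | Systolic pressure below 120 mmHg | Covered |
| Severe hypovolaemia | Systolic pressure floor only | Indirect |

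Count: 3 covered + 1 partly covered + 1 indirectly covered + 2 without a match = 7. Of the two without a match, raised intracranial pressure bears on a group that the plan recruits deliberately: "20 with intracerebral haemorrhage (for safety) (10 randomised to GTN, 10 randomised to sham". That leaves one contraindication with no criterion, no proxy and no stated reason.

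Three further checks:

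1. **Is the blood pressure floor a proxy?** No. It excludes only on measured systolic pressure, and a patient with obstruction can present at or above 120 mmHg.
2. **Is there a catch-all?** None of the 14 exclusions refers to contraindications in general or lets the investigator exclude a patient judged unsuitable. The inclusion criteria do not cover the condition either.
3. **Does the reference to the product's SmPC fill the gap?** No. The Description of the product cites it for chemical and pharmacological properties and does not tell sites to exclude on it.

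**The case against.** The strongest reply is that the contraindication is not hidden. It is printed in the same Protocol that sites must follow. The initial approach comes from the usual care team (Recruitment). A pack can be assigned and left unused, with the reason given on a Use/Non-use Form (Storage, dispensing and return). Any treating clinician may stop the study medication (Removal of participants from therapy or assessments). All of this stands, and it lowers the risk. But each safeguard depends on someone recalling the contraindication and choosing to act; none is an entry rule.

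Several stronger readings are tempting and are not supported:

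- **Any known valve stenosis is contraindicated.** The text concerns myocardial insufficiency caused by obstruction, which is a narrower group.
- **Sites must enrol such a patient.** The sentence "All participants eligible for inclusion will be randomised centrally using a secure internet site in real-time" describes how allocation is done. It does not oblige a site to enrol everyone who meets the list.
- **Enrolling such a patient could never count as a violation.** One example is "Participant enrolled in spite of not fulfilling all the inclusion and exclusion criteria", and none names the contraindications, but the Protocol says its examples are not exhaustive.
- **Such patients could not be identified at baseline.** SAP Table 1 has no row for valvular or pericardial disease, but it is a table shell. The case report form is not among the documents, and medical records are source documents.
- **Raised intracranial pressure is a second, equal gap.** ICH enrolment is a stated choice, the Background discusses possible harm in ICH with treatment before two hours, and the DMC monitors ischaemic stroke and ICH separately.
- **The concomitant-treatment sentence is a safety hole for PDE5 inhibitors.** Recent users are excluded at entry and treatment lasts two days, so this is a matter of consistent wording.

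**Conclusion.** The gap is real and narrow. Among the seven listed contraindications, myocardial insufficiency due to obstruction is the only one with no criterion, no proxy and no design reason. A patient known to have it, with a systolic pressure of at least 120 mmHg and otherwise suitable, meets the listed criteria. Existing protection is partial and discretionary.

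The conclusion rests on the text of the three exclusion lists and the contraindication list, and on no numerical assumption. How many patients it concerns cannot be estimated, because the documents give no prevalence; it is probably few. No endpoint, sample size or analysis is affected. This is a low-cost improvement worth considering, not a fault that threatens the trial's conclusions.

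**What to change.** Add one exclusion to the Protocol Synopsis, the Protocol's Exclusion criteria section and SAP section 20b, for example: *Known obstructive cardiac disease causing myocardial insufficiency (such as aortic or mitral stenosis, or constrictive pericarditis), known severe hypovolaemia, or known hypersensitivity to organic nitrates.* Add a matching eligibility item to the eCRF. The second and third parts close the indirect and partial matches in the table above.

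The line should name the conditions and not import the whole contraindication list. A blanket reference would bring in raised intracranial pressure and leave it unclear whether patients with ICH or a large infarct remain eligible.

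The cost is one text amendment and one form item. Limiting the line to known conditions means no new test. The downside is a few extra screen failures in a trial with a two-hour enrolment window, and the line does not help where the history cannot be obtained. If recruitment has closed, the line belongs in the criteria of the definitive trial.

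An optional consistency edit is to add an exception for PDE5 inhibitors while the patch is in place to the sentence on concomitant treatments.
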